3.13 Prior and Concomitant Medications

Medications used in this study will be coded by using the World Health Organization Drug Dictionary Enhanced and categorized as the following:

- Prior medication: Any medication that started before the first dose of study drug, independently of when it ended.
- Concomitant medication: Medication continued or newly received at or after first dose of study drug to the last follow-up (4 weeks after the last dose of study drug).
- Post-treatment medication: Medication continued or newly received after the last follow-up (4 weeks after the last dose of study drug).

A given medication can be classified using the above, in one or more categories. If a medication has a missing or partial missing start/end date or time and cannot be determined whether was taken before the first dose of study drug, concomitantly, or after 4 weeks after the last dose of study drug,

it will be considered as prior, concomitant, and post-treatment. Prior medications and concomitant medications will be summarized descriptively based on the ITT population. Post-treatment medications will be listed for each patient.

3.14 Analysis of the Primary Efficacy Endpoints

The study will be considered successful if a statistically significant advantage for fenretinide over placebo is obtained for the absolute change in FEV₁ percent predicted from baseline to Week 24, as assessed in the ITT population. Confirmatory analyses will be conducted in the PP Population, Protocol-defined PEx Population and Overall PEx Population.

Values for percent predicted FEV₁ as well as their change relative to baseline will be tabulated by time point and descriptive statistics will be used. In the analysis of the primary efficacy endpoint, the absolute change from Baseline in FEV₁ percent predicted, including all measurements up to Week 28 (both during and after treatment measurements, including after treatment discontinuation) will be analyzed based on a mixed model for repeated measures, with the following specifications:

- The dependent variables will be all the absolute changes in FEV₁ percent predicted from Baseline to each time point, including Week 28;
- The fixed effects will be the treatment group, the visit and the treatment-by-visit interaction;
- The random effect will be the patient;
- An unstructured variance-covariance structure will be adopted as the default structure; alternate variance-covariance structures may be adopted as appropriate.
- The model will be adjusted for the following *à priori* stratification categories:
 - FEV₁ percent predicted determined at Baseline (<70% versus ≥70% predicted),
 - PEx frequency in the prior year (≤3 versus > 3 PEx episodes),
 - Co-administration or not of Kalydeco® (ivacaftor), Orkambi® (ivacaftor/lumacaftor), Symdeko® (ivacaftor/tezacaftor) or another commercially available CFTR modulator product (yes versus no);

- The difference between treatment means at each time point and its 95% confidence interval will be estimated.
- Stratum-specific estimates based on Least Square Means will be generated

The primary result obtained from the model will be the treatment effect at Week 24. The estimated mean treatment effect, a 95% confidence interval, and a 2-sided p-value will be generated.

The analysis will be repeated with the addition of the following covariates in the model:

- Baseline use of Trikafta (yes versus no);
- Effect of the pandemic confinement (pre versus post pandemic onset) (described in Section 3.14.1)

Alternative methods will be used if necessary due to data not meeting the standard requirements for the proposed analysis.

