7.3.3 Randomization Scheme and Stratification

Computer-generated randomization sequences will be programmed into the IWRS. At the time of Randomization during Visit 2, not before, the IWRS will assign a randomization number to each patient.

Randomization will be stratified by

- 1- FEV₁ severity collected at the Screening Period (<70% versus ≥70% predicted);
- 2- Number of PEx (all PEx episodes, whether treated by oral or IV antibiotics): ≤3 versus > 3 PEx episodes in prior year; and
- 3- Co-administration or not of Kalydeco® (ivacaftor), Orkambi® (ivacaftor/lumacaftor), Symdeko® (ivacaftor/tezacaftor) or another commercially available CFTR modulator product.

Once stratified, patients will be randomized in a 1:1 double-blinded fashion to either LAU-7b (active) group or the placebo (control) group. Stratification will enable an even distribution of severity and key baseline characteristics among the two treatment groups.

Detailed instructions for randomization will be provided separately.

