9.2.2 Baseline and First Dosing Visit (Visit 2, Day 1)

1. Eligible CF patients will be invited to the study site for the baseline procedures and first dosing. This visit must be within 28 days of screening otherwise all or a part of expired screening procedures will need to be repeated/updated (see Section 9.2.1.2);
2. Confirmation of continued eligibility by verification of the inclusion/exclusion criteria, review of the results of the screening safety laboratory tests including plasma retinol and retinol-binding protein, performance of baseline vital signs, urine pregnancy test for women, and focused physical examination;

3. Pulmonary function tests (FEV₁). The actual baseline FEV₁ value for the study will be the average of the screening's best value and the best value obtained during the baseline visit as long as the screening and baseline FEV₁ values are within 15% of each other. A higher difference in FEV₁ % predicted indicates a lack of acceptable pulmonary function stability and the patient should not be randomized on study;
4. Body weight, with BMI calculated;
5. At sites that participates in the bone density exploratory assessment, the first 24 patients who consent to the additional procedure of measuring bone density prior to and after the study treatment, will undergo their baseline assessment; being not exclusionary, this test may be scheduled within a few days of first dose but not after;
6. Baseline Quality of Life questionnaire will be filled out (CFQ-R);
7. At select sites participating in the investigation of the Matouk Disease Score, the Baseline Score will be determined;
8. Pre-dose blood sampling and urine collection for baseline safety laboratory tests, pregnancy test if applicable, plasma retinol and retinol-binding protein, lipidomic tests, ceramides, metabolipidomic tests, systemic bone formation/resorption markers, inflammation and oxidative stress markers;
9. All eligible patients will be stratified according to 1- Baseline FEV₁, 2- PEx number in the prior year, and 3- Co-administration of Kalydeco® (ivacaftor), Orkambi® (ivacaftor/lumacaftor), Symdeko® (ivacaftor/tezacaftor) or another commercially available CFTR modulator product, and equally allocated/randomized to either a daily dose of 300mg of LAU-7b, (as 3 x 100 mg oral hard gelatin capsules), or matching placebo.

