12 STATISTICAL ANALYSIS

A statistical analysis plan (SAP) will provide details of the methods of analysis to address all study objectives. The SAP may be amended during the course of the study, but will be finalized before the cutoff date for any analysis.

Data summaries by treatment group will be presented. For continuous variables, data will be summarized with the number of patients, mean, standard deviation, median, and minimum and maximum values by treatment group. For categorical variables, data will be tabulated in frequency tables to display the number and proportion of patients for each category by treatment group. Baseline assessments for each outcome variable will be defined as the last measurement obtained before the first dose of study drug except the baseline FEV₁ which will be the average of the screening and baseline best values, to reduce variability. Statistical significance will be set at the 5% level.

Diligent efforts will be made to prevent missing data in the study. For example, patients who discontinue the study treatment early or initiate medication changes (including those prohibited by the protocol) should still be followed for all regularly scheduled visits for safety and relevant efficacy assessments, or for a minimum of a 1-month follow-up. A clear distinction should be made between treatment discontinuation and study withdrawal. Efficacy assessments occurring after treatment discontinuation should not be included in the per-protocol analysis.

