12.4 Efficacy Analysis

12.4.1 Analysis of Primary Endpoint

The study will be considered successful if a statistically significant advantage for fenretinide over placebo is obtained for the absolute change in FEV₁ percent predicted from baseline to Week 24.

Values for percent predicted FEV₁ as well as their change relative to baseline will be tabulated by time point and descriptive statistics will be used. In the analysis for the primary efficacy endpoint, change from baseline in FEV₁ % predicted (absolute change), including all measurements up to Week 28 (both during and after treatment measurements, including after treatment discontinuation) will be analyzed based on a mixed-effect repeated-measure model. Even though no imputations will be used in the primary analysis, a sensitivity analysis will be conducted where missing data points will be imputed using appropriate interpolation methods; extrapolation methods will be used for truncated FEV₁ % predicted values.

The planned model will include the absolute change from baseline in FEV₁ % predicted as the dependent variable; treatment, visit, and treatment-by-visit interaction as fixed effects; and patient as a random effect with adjustments for a) FEV₁ % predicted determined at the Screening/Baseline Visits (average where possible), b) PEx frequency in the prior year, and c) Co-administration or not of Kalydeco® (ivacaftor), Orkambi® (ivacaftor/lumacaftor), Symdeko® (ivacaftor/tezacaftor) or another commercially available CFTR modulator product. Additional post-hoc analyses may be performed in an exploratory manner depending on the frequency of other phenotypes or concomitant drugs. The primary result obtained from the model will be the treatment effect at Week 24. The estimated mean treatment effect, a 95% confidence interval, and a 2-sided P value will be generated. Alternative methods will be used if necessary due to data not meeting the standard requirements for the proposed analysis.

Full details will be specified in the SAP.

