12.4.2 Analysis of Secondary Efficacy Endpoints

For all secondary efficacy endpoints, the primary analysis will be based on data obtained at Week 24 or cumulated up to Week 24.

Pre-defined Clinical Parameters:

- Count data variables: The time to first antibiotic use, the number of antibiotic treatments, the number of days of antibiotic treatment (other than chronic inhaled antibiotics already started prior to trial or oral chronic azithromycin) and the number of protocol-defined PEx will be tabulated by treatment and compared using Count regression will be used for the group comparison of the number of antibiotic treatments and the number of days of antibiotic treatment. The number of protocol-defined PEx will take

into account in the model of the time spent on study and considering the same covariates as those described below for the time to event data.

- Time to event data variables: The time to first protocol-defined PEx, the time interval between IV antibiotic-treated PEx episodes will be tabulated by treatment and compared using a Cox proportional hazards regression analysis. The model will include treatment as main effect with covariates for age category at baseline, FEV₁ % predicted category (as per entry stratification), PEx number category in prior year (as per entry stratification). A patient without exacerbation before withdrawal or completion of the study is considered censored at the time of withdrawal or completion of the study. If the proportional hazards assumption is violated, a stratified analysis will be conducted using stratified Cox regression. Additionally, Kaplan-Meier methods will be used to produce graphical presentations of the survival (exacerbation-free survival) by treatment and to estimate cumulative survival rates by treatment.
- Relative change (in %) in FEV₁ % predicted from baseline to Week 24: Analysis of this variable will be similar to that of the primary analysis of the primary efficacy endpoint
- Body weight and BMI changes from baseline/screening will be summarized using descriptive statistics by treatment and compared between treatments using a linear mixed-effects model with treatment as fixed effect; visit and treatment-by-visit interaction as random effects; and adjustment for FEV₁ % predicted category (as per entry stratification), PEx number category in prior year (as per entry stratification) and weight or BMI at baseline as covariates.

Pharmacodynamic Endpoints:

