- Body weight and BMI changes from Baseline/Screening will be summarized using descriptive statistics by treatment group and compared between treatments using a linear mixed model similar to what is described under [Section 3.14](#), with the addition of the baseline parameter (Weight or BMI at baseline) as covariate in the model.

Quality of Life Endpoints:

- Quality-of-life data will be derived from the questionnaires according to the corresponding scoring manuals and will be summarized by treatment group. Patients' health state will be derived from the CFQ-R questionnaire, including the extracted CFQ-R respiratory domain, a separate endpoint. Additional exploratory health condition will be evaluated by the Matouk Disease Score. Data will be summarized by treatment group using descriptive statistics.

Analysis of the absolute change from baseline for the CFQ-R (overall and respiratory domain) as well as the Matouk Disease Score will be performed similarly to that of the primary efficacy endpoint with the addition of the CFQ-R score at baseline as a covariate for the analysis of the CFQ-R variables.

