3.17 Analysis of the Pharmacokinetic/Pharmacodynamics Endpoints

Pharmacodynamic Endpoints:

Values for AA, DHA and AA/DHA ratio as well as their change relative to baseline will be tabulated by time point and descriptive statistics will be used. The rate (frequency) of normalization (normalization meaning a parameter value reaching the mean parameter value observed in healthy controls ± 1 Standard Deviation) for AA, DHA, and the AA/DHA ratio will be calculated for the end-of-treatment cycle values, and the treatments will be compared using two-sided multivariate logistic regression with the respective baseline value as a covariate. Alternative methods will be used if necessary due to the data distribution. Healthy controls will consist of a group of approximately 20 healthy, non-CF adult subjects of both genders, not specifically matched to the APPLAUD CF patients.

Values for pharmacodynamic parameters (AA, DHA and AA/DHA ratio), EPA, inflammation markers, metabolipidomic markers, systemic bone formation/resorption markers, markers of oxidative stress, ceramides), as measured in plasma (or serum, or blood, as required), as well as their change relative to baseline, will be tabulated by time point and descriptive statistics will be used. An analysis of variance will be used to compare treatments assuming datasets meet standard pre-requisites for such analysis (normal or log-normal distribution and homogeneity of variance). Alternative methods will be used if necessary.

Pharmacokinetic Endpoints:

Blood samples for fenretinide C_{\min} analysis will be obtained from all patients randomized to fenretinide. Patients randomized to placebo will provide samples (to maintain the study blind) but will not contribute to the C_{\min} data.

Plasma fenretinide C_{\min} concentrations will be presented in a tabular summary, by sampling day and compared between groups of CF patients receiving fenretinide grouped according to the a-priori stratification factors, and assuming stratum size will allow such comparison.

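### SAP 3.14 swaps the protocol's baseline FEV₁ value for a two-level category in the primary model without logging it, and the SAP 3.17 biomarker ANOVA names no baseline covariate; both give up some precision

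*SAP*

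**What the plan says.** **Primary model.** Protocol 12.4.1 and the synopsis adjust for "FEV₁ % predicted determined at the Screening/Baseline Visits (average where possible"). Protocol Section 12 defines baseline FEV₁ as the "average of the screening and baseline best values, to reduce variability". SAP 3.14 instead adjusts for the stratification categories, with FEV₁ entered as "FEV₁ percent predicted determined at Baseline (<70% versus ≥70% predicted"). No continuous FEV₁ term remains.

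**Where the protocol means a category.** For the Cox and weight/BMI models, Protocol 12.4.2 writes "FEV₁ % predicted category (as per entry stratification").

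**Change log.** One row of SAP Section 5 cites Protocol 12.4.1, and it adds the Trikafta and pandemic covariates. Another row clarifies that ITT decides success. No row in Sections 5 or 6 mentions categorising FEV₁.

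**Which FEV₁ sets the stratum.** Protocol 7.3.3 stratifies on "FEV₁ severity collected at the Screening Period (<70% versus ≥70% predicted"). Protocol 9.2.2 says "All eligible patients will be stratified according to 1- Baseline FEV₁", and Protocol 7.2.1 and SAP 3.14 also say baseline.

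**Other outcomes.** For weight and BMI, SAP 3.15 uses a similar model "with the addition of the baseline parameter (Weight or BMI at baseline) as covariate in the model", and it does the same for the CFQ-R. In SAP 3.17 the AA, DHA and AA/DHA normalization regression carries its baseline value. For biomarker values and changes, however, the section says only "An analysis of variance will be used to compare treatments", with no covariate. That ANOVA covers the inflammation markers, which are a secondary endpoint.

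**The concern.** The primary model alone decides whether the study is positive (SAP 3.2 and 3.14). A covariate change there should appear in the section that exists to record departures from the protocol. Cutting a continuous prognostic measure in two discards part of what it explains, so the confidence interval is somewhat wider than it needs to be.

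The FEV₁ term is also not uniquely defined. A patient with 68% at screening and 76% on Day 1 averages 72%: below the cut by the screening value, above it by the averaged baseline. Two programmers could code the deciding model differently.

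The biomarker comparisons are signal-detection analyses at nominal alpha. Leaving out each marker's own baseline makes a real signal easier to miss, and the SAP already makes this adjustment for weight, BMI, CFQ-R and lipid normalization.

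**Working it through.** **Inputs from the documents:** difference 4, SD of change 8, 60 completers per group, 136 randomized (Protocol 12.1, SAP 2.6); two-sided 5% (SAP 3.1.1); screening FEV₁ 40–100% predicted; cut at 70%.

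**Assumed, because the documents do not give them:** baseline FEV₁ SD of 12 to 17.3 (17.3 is the SD of a uniform distribution on 40–100); biomarker baseline-to-follow-up correlation r of 0.3 to 0.8.

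**The plan's own figure.** With difference 4 and SD 8, a two-sided t-test at 60 per group has 77.5% power, and 80% needs 64 per group (63 by normal approximation). So 60 is not reproduced. That is a separate matter, but it shows there is no surplus power without covariate gain.

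**Step 1. Share of the variance of change explained by continuous baseline FEV₁ (R²).**

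*(a) Baseline and follow-up with equal variance.* The slope of change on baseline is −32/SD², so R² = (32/SD²)² × SD²/64 = 16/SD².
- SD 12: 16/144 = 0.111
- SD 17.3: 16/300 = 0.053

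*(b) Baseline as a two-visit average, with independent visit errors of variance s² and no true change.* Var(change) = 1.5s² = 64, so s² = 42.7 and the baseline error variance is 21.3. Then R² = 21.3²/(64 × SD²).
- SD 12: 0.049
- SD 17.3: 0.024

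**Step 2. Share of that R² kept by the 70% split.** It is 0.75 if baseline is uniform on 40–100, and 2/π = 0.637 if it is normal and centred at 70.

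**Step 3. Residual variance, category over continuous** = (1 − kept × R²)/(1 − R²). For each model of baseline, the two ends of the range are:

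| Model | SD, share kept | Ratio |
|---|---|---|
| (a) | 12, 0.637 | 0.929/0.889 = 1.045 |
| (a) | 17.3, 0.75 | 0.960/0.947 = 1.014 |
| (b) | 12, 0.637 | 0.969/0.951 = 1.019 |
| (b) | 17.3, 0.75 | 0.982/0.976 = 1.006 |

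The overall excess is 0.6% to 4.5%.
- Patients: 136 × 0.006 = 0.8, up to 136 × 0.045 = 6.2.
- Interval width: √1.006 = 1.003 and √1.045 = 1.022, so 0.3% to 2.2% wider.

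**Step 4. Power at 60 per group** (t-test with the residual SD from each model, category versus continuous).
- Largest gap: 80.45% vs 82.15%, 1.7 points.
- Smallest gap: 78.25% vs 78.50%, 0.24 points.

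**Cross-check on a correlation scale.** Assuming correlations between baseline and change directly, with 0.64 kept, the loss is 0.6 points at 0.2, 1.4 at 0.3, 2.4 at 0.4 and 3.8 at 0.5. It is nil at zero. The R² values in Step 1 correspond to correlations of about 0.15 to 0.33 (√0.024 to √0.111).

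**Step 5. Biomarkers, variance relative to ANCOVA** (equal variances at both times). Change scores: 2(1 − r)/(1 − r²). Raw values: 1/(1 − r²).

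| r | Change | Values |
|---|---|---|
| 0.3 | 1.54 | 1.10 |
| 0.5 | 1.33 | 1.33 |
| 0.8 | 1.11 | 2.78 |

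**The case against.** **Delegated detail.** Protocol 12.4.1 never says continuous, names the three randomization factors, and leaves full details to the SAP. The prior-year exacerbation count is just as unqualified there and is also dichotomised in SAP 3.14. An averaged value could itself be split at 70%. This makes the reading an inference, but the better one: the protocol asks for an average of two measurements, and it uses the word category when it wants the stratum.

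**Legitimate model.** Adjusting for stratification factors is sound and supports the planned stratum-specific estimates. That stands. Adding the continuous value keeps those terms and estimates.

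**Negligible size.** The upper figures rest on equal variances. Under the two-visit model, which is closer to the protocol's baseline definition, the loss is 0.24 to 0.74 power points. The category model still beats the unadjusted t-test used for sizing (77.5%), so nothing the plan counted on is lost. This stands and limits the point's weight, although the two-visit model also depends on independent visit errors.

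**Biomarkers.** The ANOVA comes from the protocol, so it is not a SAP departure. The inflammation endpoint is a change from pre-study, and the SAP does not say outright that raw values are tested, so the 2.78 ratio may not apply. For change the range is 1.11 to 1.54. These tests are nominal and for signal detection. All of this is fair. The avoidable loss on change scores remains.

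**Alternative-methods clauses.** In SAP 3.14 and for the ANOVA in SAP 3.17 these are tied to data not suiting the planned method. They do not supply a baseline covariate.

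**Conclusion.** The concern holds. SAP 3.14 uses a two-level FEV₁ term where Protocol 12.4.1 describes a value, the change is not logged, and the FEV₁ value behind the stratum is described in two ways. The biomarker ANOVA has no named baseline covariate.

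No bias follows from either choice. The FEV₁ cost is small: 0.6% to 4.5% of residual variance and 0.2 to 1.7 power points at 60 per group, resting on an assumed baseline SD and error structure. It would vanish if baseline were unrelated to change. The biomarker cost can be larger: 11% to 54% extra variance on change scores for assumed correlations of 0.8 down to 0.3. The change is worth making because the first part concerns the model that decides success and because it costs almost nothing.

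**What to change.** - **SAP 3.14:** add baseline FEV₁ % predicted as a continuous covariate, using the screening/Day 1 average, alongside the strata as randomized. State whether the FEV₁ stratum is the screening value of Protocol 7.3.3 or the averaged baseline.
- **SAP 3.17:** replace the ANOVA with ANCOVA on each marker's own baseline value, on the log scale where the marker is log-normal.
- **SAP Section 5:** record both changes.

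The cost is SAP wording, two rows in Section 5 and one degree of freedom per model. All the values needed are already collected.
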